#### **4.6.2 Adverse Events**

The original terms recorded on the eCRF by the Investigator for AEs will be assigned by the Sponsor to a standardized term (the “preferred term”) based on MedDRA. All data displays of AE will be performed using the system organ class and preferred terms. All AEs will be presented as frequency tables by randomized treatment arm with numbers and percentage of participants experiencing AEs.

AEs will be separately summarized for the following analysis periods:

- Screening/Wash-out period for antipsychotics includes the AEs with onset before the first day of study medication in the randomized double-blind treatment period (Baseline Sign and Symptoms).
- Double-blind treatment period including follow-up includes all AEs from day of first onset of study medication in the double-blind treatment period until end of follow-up.

Intensity and relationship to study treatment will be summarized for the double-blind treatment period including follow-up as assigned by the investigator.

In the summary table of AEs by intensity, if a participant has more than one occurrence of an event, the event with the most severe intensity will be counted. If the intensity of an AE is missing, then the AE will be included only in the total number of events column and not in the count of participants with the event by intensity.

In the summary table of AEs by relationship to trial treatment, if a participant has more than one occurrence of an event, the most closely related event will be counted. If the relationship of an AE is missing, then the AE will be included only in the total number of events column and not in the count of participants with the event by relationship.

All SAEs and AEs that led to death, and AEs that led to withdrawal of study treatment will also be summarized by treatment arm.

The following rules will be applied for AEs with missing onset or end dates:

- Events that are missing both, onset and end dates, will be considered as emerging from treatment, given the participant had at least one dose of study medication.
- If the onset date is missing and the end date is on or after the first dosing date, then the event will be considered as emerging from treatment.
- If the end date is missing and the onset date is on or after the first dosing date of a specific period, then the event will be considered as emerging from treatment.
- If the end date is missing and the most extreme intensity is worse than the initial intensity and the onset date is before the first dosing date of a specific period, then the event will be considered as emerging from treatment.
- If the onset or end dates are missing, the duration will be set to missing.

The analysis will be based on the safety analysis population grouped according to the treatment assigned at randomization.

Time to onset of exacerbation of schizophrenia (AE preferred terms Schizophrenia, Psychotic disorder) will be evaluated by summary statistics.

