- 10 One additional sample should be taken two hours (± 0.5) post-dose.
- 11 Samples can be taken at any time between baseline and follow-up.
- 12 The Study Phone Usage Tracker will be used only with screened patients who have suitable smartphones and agree to the assessment.
- After informed consent, but prior to initiation of study drug, only SAEs caused by a protocol-mandated intervention will be collected. After initiation of study drug, all adverse events, regardless of relationship to study drug, will be reported until 28 days after the last dose of study drug.
- 14 The placebo compliance period will start with a visit reviewing instructions with the patient.
- 15 Study drug is three capsules administered once daily, preferably in the morning. The last dose is given at the Day 84/EOT visit.
- 16 Sleep, mood, cognition and treatment expectation questions will be presented on the AiCure app at select time points that will appear as random to the participant.
- 17 The exploratory endpoints Brief Assessment of Cognition in Schizophrenia (BACS) (digital version), Wechsler Abbreviated Scale of Intelligence Second Edition (WASI-II), Wide Range Achievement Test (WRAT-4) and Virtual Reality Functional Capacity Assessment Tool (VRFCAT) are not available as validated Spanish translation. Therefore, sites will not be required to administer these tests to Spanish only speaking patients. If validated versions become available, they may be used.

Table 2 Schedule of Activities for Part B of the Study

Period	Scre	ening																
		Placebo Compliance ¹ 4							Treatment								Follow Up Vis	its
Week	Week -5 to -2	Week -1	1	ı	2	3	4	5	6	7	8	9	10	11	12	13	14	15
Day	Day -35 to Day -8	Day -7	Baseline ¹ / Day 1	Day 7	Day 14	Day 21	Day 28	Day 35	Day 42 ¹	Day 49	Day 56	Day 63	Day 70	Day 77	Day 84/ EOT ^{1, 2}	Day 91	Day 98	Day 112 ²
Visit Window (days) ²⁰		±1	-1	Ħ	±1	±1	±2	±2	±2	±2	±2	±2	±2	±2	±2	±2	±2	±4
On-site visit	Х	х	х	Х	х		х		Х		Х				Х			Х
Phone Call						х		х		х		х	х	х		х	х	
Informed Consent	Х																	
Inclusion/exclusion criteria	Х		X 3															
Eligibility Checklist Form Submission	•																	
Randomization			х															
Demography	Х																	
Medical History	Х																	
Physical Examination ^{4 16}	X ²³	х	X ²³	Х	Х		Х		Х		X ²³				X ²³			X ²³
ECG-12 lead ^{5 16}	Х		Х	Х	Х		Х		Х		Х				Х			Х
Meal time ¹⁶	х		х		Х						Х				Х			х
Vital Signs ¹⁶	Х		х	Х	х		х		Х		Х				Х			Х

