To evaluate the PK of RO6889450 and RO6889450-derived metabolite(s).	
 
Concentration per time point
 
AUCss of RO6889450 and RO6889450-derived metabolite(s)
 
Cmax of and RO6889450-derived metabolite(s)
 
Other PK parameters as appropriate
 

Tertiary/Exploratory	
To explore the effects of RO6889450 on: 
 
Reward learning tasks (Effort-Choice Benefit (ECB) task; Reinforcement Learning Working Memory (RLWM) task)
 
	
 
ECB: Percentage of high effort choices under deterministic reward conditions for high reward magnitudes
 
RLWM Learning Phase: Proportion of correct choices in late trials and for large blocks of sizes
 
RLWM Testing Phase: Interaction 'value difference modulated by value mean' (assessing the 'choose A avoid B' paradigm).
 

To explore the effects of RO6889450 on: 
 
Overall functioning/cognition
 
	
 
Change from baseline in Brief Assessment of Cognition in Schizophrenia (BACS)
 
Change from baseline in adjusted total time as measured by the Virtual Reality Functional Capacity Assessment Tool (VRFCAT)
 

To explore the effects of RO6889450 on: 
 
Changes in smoking dependence
 
	
 
Change from baseline in Fagerstrom Test for Nicotine Dependence (FTND) total score
 

To explore the effects of RO6889450 on: 
 
Levels and patterns of social and general activity
 
To assess CYP2C19 status on PK parameters
 
	
 
Phone usage behavior data
 
Genotyping of CYP2C19
 

Objectives	Endpoints

 
Part A only: To assess effects on relapse prevention
 
	
 
Compare rate and timing of relapses and study withdrawal between placebo and RO6889450
 

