## 4.2 ANALYSIS OF STUDY CONDUCT

### 4.2.1 Disposition of Participants

For all patients in the modified ITT analysis population enrollment in the study, discontinuation of study drug and from the study, and reason for discontinuation will be summarized per treatment arm to which participants are randomized. In addition, protocol violations will be summarized by treatment arm.

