#### **4.5.2 Secondary Efficacy Endpoints**

Descriptive summary statistics will be presented for all secondary efficacy endpoints by visit and treatment arm for the modified ITT analysis population by treatment arm to

which participants were randomized. The same descriptive summary statistics and will be presented for the change from baseline.

Descriptive summary statistics will include the number of patients contributing to the summary statistic as well as the mean, median, lower and upper quartile, standard deviation, minimum and maximum.

In general, if at least one item score is missing or not ratable, the total/factor/subscale scores that include the item will be set to missing.

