### 4.6.1 Exposure of Study Medication

The following extent of exposure to randomized study medication will be summarized by randomized treatment arm:

- Duration of treatment (weeks), which will be calculated from the first day of randomized double-blind study medication intake as recorded with AICURE to the last day of randomized double-blind study treatment intake as recorded with AICURE, i.e. last dosing date minus first dosing date plus 1 day (divided by 7 to get weeks).
- Number of doses over the whole double-blind treatment period derived from the number of days at which randomized double-blind treatment was taken as recorded with AICURE.
- Total cumulative dose (mg) over the whole double-blind treatment period as

recorded with AICURE.

- Extent of compliance with randomized double-blind treatment (%). Treatment compliance for each participant will be calculated as actually taken dose divided by planned dose of double-blind treatment. The actually taken dose will be the total cumulative dose. The planned dose is the cumulative planned dose over 84 days, i.e., [REDACTED] x84 days.

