#### **4.7 MISSING DATA**

Generally, in summaries, all data from the respective analysis population regardless of completeness by Week 12 will be included; participants who have taken the study medication or have visited the sites only partially will be included in the summaries. No imputation will be applied for missing data will be applied.

For all rating scales, if any item score contributing to the total/factor/subscale score is missing, then the total/factor/subscale will be set to missing.

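### SAP Table 1 keeps a Part A endpoint on timing of relapse and study withdrawal, but the only relapse-timing summary ignores event-free participants and withdrawal timing is not analysed

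*SAP*

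**What the plan says.** SAP Table 1 gives a relapse-prevention objective for Part A only, with the endpoint "Compare rate and timing of relapses and study withdrawal between placebo and RO6889450". That has four parts: rate and timing, each for relapse and for study withdrawal.

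None of the efficacy subsections (SAP 4.5.1 to 4.5.4) takes it up. Relapse timing appears once, at the end of SAP 4.6.2: "Time to onset of exacerbation of schizophrenia (AE preferred terms Schizophrenia, Psychotic disorder) will be evaluated by summary statistics". For the secondary endpoints, SAP 4.5.2 explains what such a summary contains: "Descriptive summary statistics will include the number of patients contributing to the summary statistic as well as the mean, median, lower and upper quartile", together with spread and range. SAP 4.7 adds "No imputation will be applied for missing data" and has no censoring rule.

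A time origin and a window are implied but not stated for this measure. SAP 4.6.2 defines an analysis period, "Double-blind treatment period including follow-up includes all AEs from day of first onset of study medication", which runs to the end of follow-up. The Part A schedule in Protocol 1.3 limits earlier collection: "After informed consent, but prior to initiation of study drug, only SAEs caused by a protocol-mandated intervention will be collected".

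On withdrawal, SAP 4.2.1 states that "discontinuation of study drug and from the study, and reason for discontinuation will be summarized per treatment arm". The nearest timing measure is in SAP 4.6.1: "Duration of treatment (weeks), which will be calculated from the first day of randomized double-blind study medication intake as recorded with AICURE".

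**The concern.** Onset times among those who had an event say when events happened, given that they happened. They do not use the time that the other participants spent free of relapse. If a drug halves the risk of relapse over 12 weeks, the remaining relapses still spread over much the same weeks, so their median day hardly moves. A comparison of timing built this way could show nothing, or point the wrong way, when the risks differ.

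The event itself is also narrower than relapse as the trial handles it. Protocol 6.5.1 stops study drug on early signs of relapse requiring treatment, and Protocol 7.1.1 withdraws participants with signs of relapse or at imminent risk. Neither is tied to an adverse event term. Protocol Appendix 2 does not count expected symptoms of the disease as adverse events unless they are more severe than expected, and Appendix 3 (item 9) records worsening when the investigator judges it unexpected. A relapse that ends study drug can therefore be absent from the onset summary.

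At stake is whether a listed Part A endpoint gives readable information about relapse off antipsychotics.

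**Working it through.** **Step 1. Match each part of the endpoint to an analysis.**

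| Part of endpoint | Where analysed |
|---|---|
| Rate of relapse | Adverse event frequencies (SAP 4.6.2); reasons for discontinuation (SAP 4.2.1) |
| Timing of relapse | Onset of two adverse event terms (SAP 4.6.2), no rule for event-free participants |
| Rate of study withdrawal | Counts and reasons (SAP 4.2.1) |
| Timing of study withdrawal | None; SAP 4.6.1 times drug intake only |

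The by-visit CGI MTS and PANSS summaries (SAP 4.6.8, 4.5.2.2) show signals of relapse but do not time it.

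**Step 2. Figures the documents give.** They give no relapse risk and no sample-size figure for this endpoint. The nearest figure is the 20% in SAP 2.3, which reproduces: 100 / (1 − 0.20) = 125 randomized. It covers everyone who does not complete 12 weeks of treatment. A participant taken off drug for relapse is already in it, so it cannot be used as dropout added to relapse.

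**Step 3. Illustration, all inputs assumed.** Relapse and other dropout are taken as exponential and independent over 84 days. With 84-day relapse risk p and other dropout w:

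- λ = −ln(1 − p)/84, δ = −ln(1 − w)/84, h = λ + δ
- S = (1 − p)(1 − w), the share with neither event by Day 84
- events-only median = −ln(1 − 0.5(1 − S))/h
- crude proportion with relapse = (λ/h)(1 − S)

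| p | w | h per day | S | Events-only median (days) | Crude proportion | Implied non-completion, 1 − S |
|---|---|---|---|---|---|---|
| 20% | 5% | 0.00327 | 0.760 | −ln(0.880)/h = 39.1 | 19.5% | 24% |
| 10% | 5% | 0.00186 | 0.855 | −ln(0.9275)/h = 40.4 | 9.8% | 14.5% |
| 40% | 20% | 0.00874 | 0.480 | −ln(0.740)/h = 34.5 | 36.2% | 52% |
| 20% | 20% | 0.00531 | 0.640 | −ln(0.820)/h = 37.4 | 18.0% | 36% |

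Halving the risk moves the events-only median by 40.4 − 39.1, about 1 day, in the first pair and by 37.4 − 34.5, about 3 days, in the second. The first pair implies mean non-completion of (24% + 14.5%)/2, about 19%, close to the planned 20%. The second pair is well above it and serves as a high-risk bound.

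**Step 4. Small-sample behaviour.** SAP section 1 gives 27 randomized. A split of 14 (higher-risk arm) and 13 is assumed. Expected relapses are 14 × 0.195 = 2.7 and 13 × 0.098 = 1.3 in the first pair, and 14 × 0.362 = 5.1 and 13 × 0.180 = 2.3 in the second. Simulating 40,000 trials per pair and keeping those with events in both arms:

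| Risks | Trials with events in both arms | Events-only median tied or in wrong order | Same for Kaplan-Meier Day 84 risk | Same for crude proportion |
|---|---|---|---|---|
| 20% vs 10%, w = 5% | 70% | 48–49% | 35% | 36% |
| 40% vs 20%, w = 20% | 92% | 45–46% | 15% | 17% |

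Ranges show agreement between repeated runs. The SD of the Kaplan-Meier Day 84 risk in the second pair is about 14 and 12 percentage points.

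**The case against.** The case for leaving the plan alone is fair. The endpoint is exploratory, Part A was stopped at 27 participants, no test is planned (SAP 4 and 4.5), and the current protocol's objectives table (Protocol section 3) does not contain it. Rates are already summarized. SAP section 4 says that data are listed as well as summarized, and with 27 participants a listing can show individual timing, although it does not name onset or withdrawal dates. Treatment duration in SAP 4.6.1 is close to relapse timing for those who stop drug because of relapse. Kaplan-Meier barely improves on crude proportions in the simulation. All of this stands and limits the point to a modest improvement.

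Three stronger readings are tempting but not supported:

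- A reader might infer that the adverse event terms miss a large share of relapses. Protocol Appendix 2 also lists exacerbation of a chronic or intermittent pre-existing condition as an adverse event. A worsening that ends study drug could well qualify, and the documents give no figure for the share missed.
- A reader might infer that event-free participants could enter the onset summary with their last day on study, giving medians near the end of treatment. Nothing in SAP 4.6.2 suggests giving an onset time to someone without an onset.
- A reader might take the 20% in SAP 2.3 as dropout for other reasons. It is all-cause non-completion.

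What the objection does not remove is that SAP Table 1 promises timing, and the SAP neither specifies a usable analysis of it nor drops it.

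**Conclusion.** The point holds as a limited one. The timing half of the Part A relapse and withdrawal endpoint is not served: relapse onset is summarized without the time at risk of event-free participants, the event may be narrower than relapse as managed in the trial by an unknown amount, and study-withdrawal timing has no analysis. On the events-only reading, halving the risk shifts the median by about 1 to 3 days, and the ordering of the arms is little better than a coin toss.

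These sizes rest on assumed risks and dropout, constant hazards, independence of relapse and other dropout, and a 14/13 split. The events-only reading is the most natural one but is not stated.

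The finding does not mean that relapse in Part A goes unanalysed, since rates are covered by SAP 4.2.1 and 4.6.2. It also does not touch any primary or secondary result.

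**What to change.** In SAP 4.6.2, replace the onset sentence with the following:

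- **Event:** the first of either adverse event term, or study drug discontinuation with relapse or worsening as the recorded primary reason. Protocol 7.1.2 already has that reason documented.
- **Display:** n (%) by arm and a descriptive Kaplan-Meier estimate from first dose to Day 84, without a test.
- **Censoring:** participants without an event at last on-study contact or Day 84, whichever is earlier.
- **Study withdrawal:** the same display, or a listing with dates.

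If the sponsor judges 27 participants too few, one sentence should state that timing is not analysed in Part A, as SAP 4.5.3.7 does for CYP2C19.

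The cost is one derived variable and two small outputs, or that one sentence. The downsides are imprecise estimates, a small gain over the crude proportions already planned, dependence on how sites word the primary reason, and the Kaplan-Meier assumption that other withdrawals are unrelated to relapse risk. No clinical rule changes.

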#### **4.6.3 Clinical Laboratory Tests**

The Investigator will review the laboratory report, document this review, and record any clinically relevant changes occurring during the study in the AE section of the eCRF.

In study **Part A**, hematology, chemistry and lipids are assessed at Week -4, Day 1, Day 14, Day 42, Day 84/EOT, Day 112 (FU). Urinalysis is additionally assessed at Day 28 and Day 56, but not at Day 42. Hematology, chemistry and lipids assessments will be assigned to analysis study days according to the following table:

Assessment Day	Assigned Study Day
>88 or >= 1 day after last study medication	FU, will not be included in statistical analysis
64-88	84
28-63	42
2-28	14
-2-1	1
<-2	-35, will not be included in statistical analysis

Urinalysis assessments will be assigned to analysis study days according to the following table:

Assessment Day	Assigned Study Day
>88 or >= 1 day after last study medication	FU, will not be included in statistical analysis
71-88	84
43-70	56
22-42	28
2-21	14

Clinical laboratory data are stored on the database in the units in which they were reported. For analysis laboratory data will be converted using the International System of Units (SI units; Système International d'Unités). Laboratory data not reported in SI units will be converted to SI units before processing and will be transformed to common reference range using Roche Safety Lab Standardisation.

Summary statistics for converted values and changes from baseline at each assessment time will be presented. Baseline is the patient's last observation prior to initiation of randomized double-blind study treatment.

The number of patients with a laboratory value abnormality in the direction specified (low/high) among patients during randomized double-blind treatment without this abnormality at baseline will be summarized.

Mean (+/- SEM) plots including single values will be presented by scheduled time point and randomized treatment arm.

Safety laboratory test values will be presented by individual listing with flagging of values outside the normal range.

The analysis will be based on the safety analysis population grouped according to the treatment assigned at randomization.

#### **4.6.4        Electrocardiograms (ECG) data analysis**

Triplicate ECGs are required at screening, where the three individual ECG tracings should be obtained as closely as possible in succession, but no more than two minutes apart. The full set of triplicates should be completed in less than five minutes. At all other visits, single ECGs are collected. Any clinically relevant changes or abnormalities occurring during the study should be recorded in the AE section of the eCRF.

In study **Part A**, twelve-lead ECG recording will be obtained at Week -4, Day 1, Day 14, Day 56, Day 84/EOT, Day 112 (FU). ECG assessments will be assigned to analysis study days according to the following table:

Assessment Day	Assigned Study Day
>88 or >=1 day after last study medication	FU, will not be included in statistical analysis
71-88	84
36-70	56
2-35	14
-2-1	1
<-2	-35, will not be included in statistical analysis

Summary statistics for actual heart rate, PQ (PR), QRS, QT, RR, and QTcF values and changes from baseline at each assessment time will be presented. Baseline is the patient's last observation prior to initiation of randomized double-blind study treatment.

The number of patients with a ECG value abnormality in the direction specified (low/high) during randomized double-blind treatment will be summarized.

QTcF intervals will be classified into categories  $\leq 450$  msec,  $>450\text{--}480$  msec,  $>480\text{--}500$  msec and  $>500$  msec, change from baseline will be classified into categories  $\leq 30$  msec,  $>30\text{--}60$  msec,  $>60$  msec; both will be summarized by scheduled time point and overall for the maximum post-baseline interval.

ECG data will be presented by individual listings. In addition, tabular descriptive summaries for the change from baseline in ECG intervals: heart rate, PQ (PR), QRS, QT, RR, and QTcF. T- and U-waves abnormalities will be displayed.

ECG data will be presented by individual listing with flagging of values outside the normal range.

Mean (+/- SEM) plots including single values will be presented by scheduled time point and randomized treatment arm.

The analysis will be based on the safety analysis population grouped according to the treatment assigned at randomization.

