9.4.3 Safety Analyses

All safety analyses will be based on the safety analysis population grouped according to the treatment assigned at randomization. Analysis methods are summarized in Table 9.

 Table 9
 Safety Statistical Analysis Methods

Endpoint	Statistical Analysis Methods
Adverse events	The original terms recorded on the eCRF by the Investigator for AEs will be coded by the Sponsor. AEs will be summarized by mapped term and appropriate thesaurus level.
Clinical laboratory tests	All clinical laboratory data will be stored on the database in the units in which they were reported. Participant listings and summary statistics at each assessment time will be presented using the International System of Units (SI units; Système International d'Unités). Laboratory data not reported in SI units will be converted to SI units before processing.
	Laboratory test values will be presented by individual listings with flagging of values outside the normal ranges.
Vital signs	Vital signs data (including orthostatic changes) will be presented by individual listings with flagging of values outside the normal ranges and flagging of abnormalities. In addition, tabular summaries or averaged graphs will be used, as appropriate.
ECG data analysis	ECG data will be presented by individual listings. In addition, tabular descriptive summaries for the change from baseline in ECG intervals: heart rate, PQ (PR), QRS, QT, RR, QTcF, T- and U-waves will be displayed
Concomitant medications	The original terms recorded on the participants' eCRF by the Investigator for concomitant medications will be standardized by the Sponsor by assigning preferred terms.
	Concomitant medications will be presented in summary tables and listings.
C-SSRS	C-SSRS data will be presented by individual listings.
ESRS-A	ESRS-A data will be presented by individual listings.

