## 1. BACKGROUND

This Technical Document for Statistical Analysis (TDSA) provides the data-handling rules, derivation rules, and statistical methods of summarizing and analyzing the efficacy and safety data that will be used for the data analysis and the reporting of the results from **Part A** of study BP40283.

Recruitment rate in **Part A** has remained substantially below the original estimates despite the implementation of a protocol amendment and the addition of more sites. Therefore the Roche TAAR1 Project Team and the Clinical Team have decided to stop study Part A (monotherapy) and start Part B (add-on treatment). In total 27 patients have been randomized into **Part A**.

There will be a separate TDSA for **Part B** of the study.

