#### **Exclusion Criteria:**

##### **Medical Conditions**

1. **Part A only:** Confirmed suicidal behavior based on Investigator judgment or violent behavior resulting in injury or property damage in the prior five years. A history prior to the last five years requires approval by the Patient Review Committee (PRC) on a case-by-case basis.
2. **Part A only:** Lifetime history of homicidal behavior
3. Moderate to severe substance use disorder within six months (excluding nicotine or caffeine) as defined by DSM-5.
4. Other current DSM-5 diagnosis (e.g., bipolar disorder, major depressive disorder).
5. PANSS item G6 (depression) greater than or equal to 5.
6. Significant risk of suicide or harming him- or herself or others according to the Investigator's judgment.
7. A prior or current general medical condition that might be impairing cognition or other psychiatric functioning (e.g., migraine headaches requiring prophylaxis treatment, head trauma, dementia, seizure disorder, stroke; or neurodegenerative, inflammatory, infectious, neoplastic, toxic, metabolic, endocrine etc. conditions).
8. Positive result at screening for hepatitis B surface antigen (HBsAg), hepatitis C (HCV, untreated), or human immunodeficiency virus (HIV)-1 and -2. HCV patients who have been successfully treated and who test negative for HCV RNA, may be considered eligible for entry into the study.
9. Tardive dyskinesia that is moderate to severe or requires treatment.
10. History of neuroleptic malignant syndrome.
11. Average triplicate QTcF interval greater than 450 msec for males and 470 msec for females or other clinically significant abnormality on screening electrocardiogram (ECG) based on centralized reading.
12. Clinically significant abnormalities in laboratory safety test results (including hepatic and renal panels, complete blood count, chemistry panel, coagulation and urinalysis), including:
  - o Aspartate transaminase (AST), alanine transaminase (ALT)  $>2 \times$  upper limit of normal (ULN)
  - o Total bilirubin  $>1.5$  ULN with the exception of Gilbert syndrome
  - o Serum creatinine  $>1.5$  ULN

In case of uncertain or questionable results, tests performed during screening may be repeated before randomization to confirm eligibility or may be accepted if they are, in the opinion of the Investigator and the Medical Monitor, not clinically significant.

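### SAP 4.6.4 counts on-treatment ECG abnormalities in both arms without regard to baseline status, unlike the laboratory rule, and plans no baseline-to-worst shift

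*SAP*

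**What the plan says.** SAP 4.6.4 plans this ECG count for Part A: "The number of patients with a ECG value abnormality in the direction specified (low/high) during randomized double-blind treatment will be summarized". The matching laboratory sentence in SAP 4.6.3 adds a condition; it counts abnormalities "among patients during randomized double-blind treatment without this abnormality at baseline will be summarized".

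Section 4.6.4 defines the reference point that such a condition would need: "Baseline is the patient's last observation prior to initiation of randomized double-blind study treatment". It also plans:
- absolute QTcF categories (up to 450, above 450 to 480, above 480 to 500, and above 500 msec), by visit and for the maximum after baseline;
- for QTcF, "change from baseline will be classified into categories" (up to 30, above 30 to 60, and above 60 msec), on the same schedule;
- summaries of values and of change from baseline for heart rate, PQ (PR), QRS, QT, RR and QTcF;
- mean plots that show single values, and listings that mark out-of-range values.

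Protocol 9.4.3 (Table 9) asks for ECG listings and then says: "In addition, tabular descriptive summaries for the change from baseline in ECG intervals". It gives no counting rule for abnormalities.

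On entry, the documents exclude "Average triplicate QTcF interval greater than 450 msec for males and 470 msec for females" (SAP Appendix 1; the same limits are in Protocol 5.2, criterion 12). They also exclude any other screening ECG finding judged clinically significant on central reading.

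**The concern.** A by-arm count of abnormalities during treatment is usually read as what arose on treatment. Without a baseline condition, it mixes abnormalities that patients brought with them and abnormalities that appeared after the first dose. The table does not let a reader separate the two.

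This matters more than usual here. Part A is small ("In total 27 patients have been randomized into" it), and SAP sections 4 and 4.5 plan description without hypothesis tests, so readers will interpret the raw counts. With so few patients, one or two people with a long-standing out-of-range value can suggest an ECG difference between the arms, or hide one. The SAP gives no reason for handling ECG and laboratory abnormalities differently.

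**Working it through.** The plan states no figure that depends on this rule, so there is nothing to reproduce. The check is a comparison of the text, followed by an illustration.

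**Step 1: the rules side by side.**

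| Output | Baseline condition? | Within-patient link to baseline? |
|---|---|---|
| Laboratory low/high count (4.6.3) | Yes | Yes, through the at-risk restriction |
| ECG low/high count (4.6.4) | No | No |
| Absolute QTcF categories (4.6.4) | No | No; by-visit counts can show Day 1, but only as a margin |
| QTcF change categories (4.6.4) | Uses baseline | Size of change only, not the starting category |

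Nothing else in 4.6.4 or in Protocol Table 9 restores the condition.

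**Step 2: can pre-existing abnormalities enter?** Yes, by three routes.
- The entry limit for women overlaps the second QTcF band by 470 − 450 = 20 msec. A woman at 451-470 msec is eligible and can fall in the above-450-to-480 band with no change at all.
- Heart rate, PR or QRS values that are out of range but not clinically significant are not excluded.
- Eligibility uses the average of triplicate screening tracings, whereas analysis baseline is normally the single Day 1 ECG. Protocol 5.3 does not re-apply the ECG criterion at baseline. An in-range screening value therefore does not guarantee an in-range baseline, in men or women.

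**Step 3: weight of one case.** Part A randomized 27 patients 1:1. The arm sizes are not given; 14 and 13 are assumed. One patient is then 1/14 = 7.1% or 1/13 = 7.7% of an arm. Any single patient carries this weight, whether the abnormality is old or new.

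**Step 4: possible inflation.** Let b be the share of patients abnormal at baseline, s the share of those still abnormal on treatment, and e the new-onset rate in the rest. None of these is in the documents; all are assumed. With N = 14:
- as written, the expected count is N × (b × s + (1 − b) × e);
- under the laboratory rule, it is N × (1 − b) × e, out of N × (1 − b) at risk.

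For b = 10%, s = 80%, e = 5%: 14 × (0.08 + 0.045) = 1.75 patients (12.5%) as written, against 14 × 0.90 × 0.05 = 0.63 of 12.6 at risk (5.0%).

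| b | s | e | As written | Laboratory rule | Carried-over share of as-written count |
|---|---|---|---|---|---|
| 5% | 50% | 5% | 1.02 (7.3%) | 0.67 of 13.3 (5.0%) | 34% |
| 5% | 50% | 10% | 1.68 (12.0%) | 1.33 of 13.3 (10.0%) | 21% |
| 10% | 80% | 5% | 1.75 (12.5%) | 0.63 of 12.6 (5.0%) | 64% |
| 30% | 100% | 5% | 4.69 (33.5%) | 0.49 of 9.8 (5.0%) | 90% |
| 30% | 100% | 10% | 5.18 (37.0%) | 0.98 of 9.8 (10.0%) | 81% |

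Over b = 5-30%, s = 50-100% and e = 5-10%, the expected count per arm is about 1.0 to 5.2 as written and 0.5 to 1.3 under the laboratory rule. The chance of at least one carried-over case in a 14-patient arm is 1 − (1 − b × s)^14. This is 0.30, 0.69 and 0.91 for b × s of 2.5%, 8% and 16%.

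**Step 5: chance imbalance.** Suppose there is no drug effect and no new onset, and carried-over cases follow independent binomials in arms of 14 and 13. The arms then differ by two or more patients with probability 0.16, 0.32 or 0.47 when 5%, 10% or 20% of patients carry an abnormality over.

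**The case against.** The strongest reply is that this count is a supplementary line and that the rest of 4.6.4 already uses baseline. The stated secondary ECG endpoint is change from baseline in the intervals, and it is analysed that way for every parameter. QTcF also has its change categories. In 27 patients, the flagged listings and single-value plots let a reader trace an out-of-range value back to Day 1. No test or power figure depends on the count. An all-patient count beside change from baseline is a defensible choice, and nothing obliges ECG to follow the laboratory rule. A pure at-risk count would also drop patients who were abnormal at entry and then worsened.

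Most of this stands and limits the size of the point. It does not restore the missing link. Listings require reconstruction by hand. Heart rate, PR, QRS, QT and RR have no change categories. The objection about worsening patients is sound, and it is the reason to pair the restricted count with a shift table.

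A reader might also infer more than the documents support:
- **That old findings are charged to the drug.** The rule is the same for placebo, and the SAP labels these as value abnormalities during double-blind treatment. Adverse events have their own emergence rules in 4.6.2.
- **That baseline QTcF is not shown at all.** The categories are summarized by scheduled time point, and Day 1 is one of the analysis days in 4.6.4. On a natural reading, each arm's baseline distribution appears. It is only a margin, however: equal counts at Day 1 and Day 56 could be the same patients, or some resolving while others newly cross.
- **That an eligible woman above 450 msec will be counted at every visit.** That assumes persistence, which the documents do not establish.
- **That the cardiovascular concern in Protocol 2.3 rests on this count.** The signal described there is pulse rate and postural tachycardia, and SAP 4.6.9 analyses standing-minus-supine heart rate separately.

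**Conclusion.** The gap is real but minor. As written, a patient out of range at baseline and unchanged afterwards counts as having an on-treatment ECG abnormality, in either arm, and no planned table shows movement from baseline QTcF category to the maximum. The result is inflated counts in both arms and exposure to chance baseline imbalance. There is no systematic bias between arms.

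The wording difference is certain. The size is not: the 7.1 to 7.7 points per patient rest on an assumed 14/13 split (stratified block randomization over 2 × 2 × 2 = 8 strata could leave a different one), and every carry-over rate used above is assumed. The stated ECG endpoint, the change-from-baseline analyses and the listings are unaffected and partly mitigate the problem. The conclusion covers Part A only; Part B has a separate analysis document that was not available.

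**What to change.** In SAP 4.6.4:
- Restrict the low/high ECG count to patients without that abnormality at baseline, by direction, and report it over the matching at-risk denominator, as 4.6.3 does for laboratory values.
- Add a shift table of baseline category by worst on-treatment category. For QTcF, use the four planned bands with the maximum after baseline. For the other ECG parameters, use low, normal and high. Patients abnormal at baseline then stay visible, including those who move to a higher QTcF band. A further move within the same low or high category would still be read from the change summaries and listings.
- Keep the planned QTcF change categories, change-from-baseline summaries and flagged listings.

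The cost is one changed and one added table shell. Baseline ECGs are already collected and defined, so no new data are needed.
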